4.4 Eligibility Criteria

4.4.1 Inclusion Criteria

To be considered eligible to participate in this study, a patient must meet ALL inclusion criteria listed below:

- 1. Pathologically proven AML (except acute promyelocytic leukemia with the t(15;17) translocation) or intermediate risk, high risk or very high risk MDS as defined by the World Health Organization (WHO) criteria or Revised International Prognostic Scoring System (IPSS-R) harboring IDH1-R132 mutations, and one of the following based on enrollment stage or treatment cohort:
 - a. Single Agent Phase 1 Cohorts including Dose-Escalation/ Dose-Expansion: AML/MDS either R/R to standard therapy, or for whom standard treatments are contraindicated
 - b. Combination (FT-2102 + azacitidine) Phase 1 Dose-Escalation/ Dose-Expansion (patients must meet one of the following):
 - i. Patients with AML that is either R/R to standard therapy, or for whom standard treatments are contraindicated
 - ii. Patients with MDS that is either R/R to standard therapy, or are treatmentnaïve, who are eligible for azacitidine therapy
 - c. Combination (FT-2102 + cytarabine) Phase 1 Dose-Escalation/Dose-Expansion Cohort: Patients ≥ 60 years with treatment-naïve AML for whom standard treatments are contraindicated
 - d. Phase 2 Cohort 1 (Single Agent) only: AML R/R to standard therapy
 - e. **Phase 2 Cohort 2 (Single Agent) only:** AML in morphologic CR/CRi after prior therapy (+/- HSCT) with residual IDH1-R132 mutation (≥ 0.01%) detected in the bone marrow
 - f. **Phase 2 Cohort 3 (Single Agent) only:** R/R AML/MDS that have been previously treated with FT-2102 **AND** for whom standard treatments are contraindicated
 - g. **Phase 2 Cohort 4 (FT-2102 + Azacitidine) only:** Patients < 60 years old with R/R AML/MDS with no prior hypomethylating agent therapy **AND** no prior IDH1 inhibitor therapy
 - h. **Phase 2 Cohort 5 (FT-2102 + Azacitidine) only:** R/R AML/MDS that have inadequately responded to or have progressed on prior treatment with a hypomethylating agent

- i. Phase 2 Cohort 6 (FT-2102 + Azacitidine) only: R/R AML/MDS that have been previously treated with single agent FT-2102 as their last therapy prior to study enrollment
- j. **Phase 2 Cohort 7 (Single Agent) only:** Treatment naïve AML patients for whom standard treatments are contraindicated
- k. **Phase 2 Cohort 8 (FT-2102 + Azacitidine) only:** Treatment naïve AML patients who are candidates for azacitidine as a first line treatment

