 - Note for Phase 2 Cohort 7 and Phase 2 Cohort 8: Treatment naïve is defined as no prior treatment for AML. Patients may have received a prior treatment for another hematologic malignancy.
- 2. Patients must have documented IDH1-R132 gene-mutated disease as evaluated by the site
- 3. Patients \geq 18 years old
- 4. Eastern Cooperative Oncology Group (ECOG) performance status of 0 to 2 (see Appendix 3)
- 5. Signed informed consent prior to beginning study and undergoing procedures
- 6. No prior solid organ allograft
- 7. Acceptable liver function:
 - a. Bilirubin ≤ 2 times upper limit of normal (ULN) (≤ 3 times ULN in patients with Gilbert Syndrome)
 - b. Aspartate transaminase (AST, also referred to as SGOT), alanine transaminase (ALT, also referred to as SGPT) and alkaline phosphatase (ALP) \leq 3 times ULN
- 8. Acceptable renal function:
 - a. Serum creatinine ≤ 1.5 times ULN or calculated creatinine clearance ≥ 50 mL/min (Cockcroft and Gault 1976)
- 9. Recovery from the non-hematologic toxic effects of prior treatment to Grade ≤ 1, or baseline value according to NCI CTCAE classification (excluding infertility, alopecia, or Grade 1 neuropathy)
- 10. Baseline OTcF < 450 msec (average of the OTcF values of screening triplicate ECGs)

Note: This criterion does not apply to patients with a bundle branch block (BBB); for patients with BBB, a cardiology consult is recommended to ensure that QTcF is not prolonged.

- 11. Negative serum pregnancy test if female of childbearing potential
- 12. For fertile men and women, agreement to use highly effective contraceptive methods for the duration of study participation and 90 days after the last dose of study medication (Section 5.6.1)
- 13. Agreement for male patients not to donate sperm and for female patients of childbearing potential not to donate ova during the study and for 90 days after the final dose of study drug (see Section 5.6.2)
- 14. **Phase 2 Cohorts 1 8 (SA and combination) only:** Pre-treatment peripheral blood and bone marrow aspirate available for retrospective central confirmation of IDH1-R132 mutation is required.

Note: Central confirmation of IDH1-R132 mutation is not required for study enrollment.

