- 23. Prisoners or patients who are involuntarily incarcerated or are compulsorily detained for treatment of either a psychiatric or physical (e.g. infectious disease) illness Note: Under certain specific circumstances, a person who has been imprisoned may be included or permitted to continue as a patient, if local regulations permit. Strict conditions apply and Forma's approval is required.

Note: Eligibility criteria waivers will not be granted.

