6 STUDY PROCEDURES

6.1 Measurements and Evaluations

See Appendix 1 and Appendix 2 for a detailed study Schedule of Events, including measurements and evaluations for the entire study period (Screening to Follow-up) presented in tabular form.

For Protocol Version 7/ Amendment 6, a reduced Schedule of Events has been introduced for all ongoing patients receiving treatment at the time of the amendment (see Appendix 1) and a new Schedule of Events has been added for patients enrolled after Protocol Version 7/ Amendment 6 (eg, patients that transfer from Cohort 1 to Cohort 3 or Cohort 6) (see Appendix 2).

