6.1.3 Screening Period (Within 14 Days Prior to Day 1)

The following evaluations will be performed to assess the patient's eligibility for the study per schedule of events:

- Complete medical history (including surgical and cardiac history)
- Leukemia and/or MDS medical history with treatment history
- Physical examination
- Height and weight
- Concomitant medication assessment
- Vital signs (temperature, blood pressure, pulse rate, and respiratory rate)
- ECOG performance status
- Serum pregnancy test (for nonsterile women of childbearing potential)
- 12-lead ECG in triplicate (should be conducted within a 10-minute period)
 - Performed as clinically indicated for patients enrolled after Protocol Version 7/
 Amendment 6

- Clinical serum chemistries
- CBC with differential and platelet count
- Bone marrow aspirate and peripheral blood (for clinical purposes), refer to the laboratory manual for details of sample collection and timing
 - o Not applicable for patients enrolled after Protocol Version 7/ Amendment 6 if collected at End of Treatment visit prior to roll-over
- Local IDH1m confirmation (this may have occurred > 28 days prior)
- Coagulation parameters (PT and PTT)
- Blood sample collection for PD analysis (See Section 6.5 for PD sampling times)
- Urinalysis
 - Not applicable for patients enrolled after Protocol Version 7/ Amendment 6
- AE monitoring
- EQ-5D-5L QOL (any time prior to first dose) (Phase 2 only)
 - o Not applicable for patients enrolled after Protocol Version 7/ Amendment 6

6.1.4 Cycle 1, Day 1

All procedures to be performed predose, with the exception of postdose PK/PD sample collection and ECG. Following completion of predose procedures, patients will receive their first dose of FT-2102.

Note: Patients will receive only a single dose of study drug (single-agent arm and combination arm) on Cycle 1 Day 1:

- Concomitant medication assessment
- Weight
- Vital signs (temperature, blood pressure, pulse rate, and respiratory rate)
- ECOG performance status
- Physical examination
- Serum or urine pregnancy test (for nonsterile women of childbearing potential)
- 12-lead ECG (predose [Phase 1 and 2], and 2 hr, 4 hr, 8 hr postdose [Phase 1 only]) in triplicate should be conducted within a 10-minute period
 - As clinically indicated for patients enrolled after Protocol Version 7/ Amendment 6
- Clinical serum chemistries
- CBC with differential and platelet count
- Urinalysis

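### Section 6.1.3 makes the screening ECG optional for patients enrolled after Version 7, although Inclusion 10 is measured on that ECG and Appendix 2 schedules it

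*Protocol*

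**What the plan says.** Four parts of the protocol bear on the same ECG in the same patients.

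- **Section 6.1.3 (Screening Period).** The listed evaluations serve to assess the patient's "eligibility for the study per schedule of events". A triplicate 12-lead ECG is on the list, with this sub-bullet: "Performed as clinically indicated for patients enrolled after Protocol Version 7"/Amendment 6.
- **Section 4.4.1, Inclusion 10.** Baseline QTcF must be below 450 msec, taken as the "average of the OTcF values of screening triplicate ECGs". The note beneath it gives one exception: "This criterion does not apply to patients with a bundle branch block (BBB"). The section opens by saying that "a patient must meet ALL inclusion criteria listed below".
- **Section 4.4.2, closing note.** "Eligibility criteria waivers will not be granted".
- **Section 6.1 and Appendix 2.** Section 6.1 states that "a new Schedule of Events has been added for patients enrolled after Protocol Version 7/ Amendment 6", with transfers from Cohort 1 to Cohort 3 or 6 as the example. In Appendix 2 the 12-lead ECG row has a plain X at Screening, a clinical-indication entry from Cycle 1 onward, and an X at End of Treatment that carries footnote j (clinical indication only).

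**The concern.** Inclusion 10 can be evaluated only if the screening triplicate ECG has been done. Section 6.1.3 tells sites that for patients enrolled after Version 7 this ECG is discretionary, while the eligibility list and the schedule for those patients both require it. The instructions cannot all be followed.

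A QTcF limit is a cardiac safety entry check. A site that takes the Section 6.1.3 sub-bullet at face value could re-enrol a patient for whom the criterion was never assessed. That would be an eligibility deviation produced by the protocol's own wording, in a protocol that allows no waivers.

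There is a smaller knock-on for analysis. ECG change is a Phase 2 secondary endpoint, and SAP Section VI.A averages the last three pre-dose ECG readings to form the ECG baseline. Without a screening triplicate, that baseline may rest on old or incomplete readings for these patients.

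**Working it through.** No arithmetic beyond a count is involved. The check compares the texts, looks for anything that reconciles them, and looks for another ECG that could stand in.

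**1. Is the ECG qualifier part of a consistent set of reductions?** Section 6.1.3 has four sub-bullets specific to patients enrolled after Version 7/Amendment 6:

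| Item in Section 6.1.3 | Instruction for these patients | Appendix 2 at Screening | Agree? |
|---|---|---|---|
| 12-lead ECG in triplicate | Only when clinically indicated | X, unqualified | No |
| Bone marrow and peripheral blood | Not needed "if collected at End of Treatment visit prior to roll-over" | Marrow X, with a footnote stating the same condition | Yes |
| Urinalysis | Not applicable | No row | Yes |
| EQ-5D-5L | Not applicable | No row | Yes |

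Three of four agree; the ECG is the one that does not. Footnote j cannot reconcile it, because it is attached to the End of Treatment X and not to the Screening X.

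**2. Does Inclusion 10 allow for roll-over patients?** It does not. Its only exception is bundle branch block. Elsewhere the protocol sets out its roll-over relaxations explicitly: Exclusion 7 exempts Cohort 1 patients re-enrolling in Cohort 6 from washout, and the marrow sub-bullet applies only if a recent sample exists. Inclusion 10 has neither kind of text.

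**3. Could another ECG supply the QTcF?** For patients enrolled after Version 7:

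- Cycle 1 Day 1 (Section 6.1.4) and Cycle 3 Day 1 (Section 6.1.19): only when clinically indicated.
- Cycle 5 onward (Section 6.1.22) and End of Treatment (Section 6.1.23): only when clinically indicated.
- The intervening visits with an ECG (Cycle 1 Days 8, 15 and 22; Cycle 2 Days 1 and 15; Cycle 4 Day 1) and Holter monitoring: not applicable.

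The Screening X is therefore the only unconditional ECG in Appendix 2. If the Section 6.1.3 sub-bullet is followed, no ECG is mandated at any point in that enrolment.

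**4. How recent is the earlier Cohort 1 record?** Under Appendix 1 the last mandatory ECG is at Cycle 4 Day 1; from Cycle 5 it is discretionary. A patient who progresses late may have had no required QTcF for months. A patient re-entering through Cohort 3 after an allogeneic transplant must also be at least 100 days past it (Exclusion 5).

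**The case against.** The strongest reply is that the protocol already points sites to the ECG. Inclusion 10 binds on its own terms, and the lead-in to Section 6.1.3 defers to the schedule of events, which for these patients is Appendix 2. A site would have to follow one sub-bullet against both the eligibility list and the schedule. This limits how often the problem would arise, and it stands as a limit on reach. It does not remove the conflict: the sub-bullet is a specific instruction to exactly these patients, and the protocol has no rule saying which text prevails.

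Second, patients transferring from Cohort 1 met Inclusion 10 at first entry and had scheduled ECGs through Cycle 4 for as long as they stayed on treatment. So what could be missing is a current value, not all knowledge of their QTcF. That is true, but Inclusion 10 asks for a screening value. Section 6.1 also offers the Cohort 1 transfers only as an example.

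Third, the ECG is not the only line in Section 6.1.3 out of step with Appendix 2. Blood sampling for pharmacodynamics has no post-Version 7 qualifier there, yet Appendix 2 has no such row. This is correct, but a note in Section 6.5 resolves that mismatch by saying the samples are no longer collected. Nothing similar resolves the ECG.

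Fourth, the same ECG reduction recurs at Cycle 1 Day 1 and Cycle 3 Day 1, so it may be deliberate. The documents do not settle the intent. If it was deliberate, Inclusion 10 and Appendix 2 are the texts that need changing.

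**Conclusion.** The contradiction is real and should be corrected. For patients enrolled after Version 7/Amendment 6, Section 6.1.3 makes discretionary an ECG that Inclusion 10 and Appendix 2 both require, and no other text reconciles them.

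Its reach is limited to patients enrolled after Version 7 at sites that follow the sub-bullet instead of Appendix 2. The documents do not give that number, and no estimate is offered. One entry check is at risk, not all cardiac screening: cardiac history, concomitant-medication review and Exclusions 11 to 13 remain. The Cohort 1 primary efficacy test is unaffected.

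The conclusion assumes that the plain X in the Appendix 2 Screening column means what it does for the other rows, namely that the procedure is required.

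**What to change.** Delete the clinical-indication sub-bullet under the ECG in Section 6.1.3, and state in Appendix 2 that the Screening ECG is in triplicate, since that row currently omits the word and Inclusion 10 depends on it. Section 6.1.4 needs no change because it already agrees with Appendix 2. This is a wording correction and adds no procedure beyond what Inclusion 10 and Appendix 2 already require.

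If a relaxation for roll-over patients was intended, amend Inclusion 10 to accept an earlier triplicate ECG with a stated maximum age, in the same conditional style as the marrow sub-bullet, and align Appendix 2. This route costs more: Section 10.6 treats a change to patient selection criteria as substantive, so it needs a protocol amendment with IRB/EC approval.

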6.1.22 Cycle 5 and Beyond, Day 1 (Every Other Cycle)

Beginning with Cycle 5, patients will return to the clinic every other cycle.

All procedures to be performed predose:

- Concomitant medication assessment
- Weight
- Vital signs (temperature, blood pressure, pulse rate, and respiratory rate)
- 12-lead ECG as clinically indicated
- ECOG performance status
- Symptom-directed physical examination
- Serum or urine pregnancy test for female patients of childbearing potential
- Clinical serum chemistries
- CBC with differential and platelet count
- Bone marrow aspirate or biopsy for response assessment
 - o For patients with AML: Every 6 cycles unless there is an indication of relapse/progression
 - o For patients with MDS: As clinically indicated
 - o For patients enrolled in Phase 2 Cohort 2: Only if there is a suspicion of relapse
- AE monitoring

Cycle 5 and beyond (every other cycle): Day 1 testing may be done within 72 hours prior to the Day 1 visit.

6.1.23 End of Treatment Assessments

The following assessments should be performed within 7 days from decision to discontinue treatment with FT-2102 (vs. discontinuation from the entire study, as detailed in Section 8.2):

- Concomitant medication assessment
- Weight
- Vital signs (temperature, blood pressure, pulse rate, and respiratory rate)
- ECOG performance status
- Physical examination
- Serum or urine pregnancy test for female patients of childbearing potential
- 12-lead ECG as clinically indicated
- Clinical serum chemistries
- CBC with differential with platelet count
- Bone marrow aspirate or biopsy (for disease assessment) as clinically indicated
- Urinalysis if medically indicated
- AE monitoring

If the patient had any of these assessments within the previous 2 weeks (4 weeks for bone marrow aspirate or biopsy), then these assessments need not be repeated.

6.1.24 Safety Follow-up Visit/Interview

All AEs will be followed for 28 days after administration of last dose of study drug or until resolution or stabilization as documented by physical examination or appropriate laboratory results. If subsequent anticancer therapy is initiated earlier, this visit or contact should occur before the initiation of subsequent anticancer therapy. The data should be documented on the appropriate eCRF page.

6.1.25 Disease Response Follow-up

Patients who discontinue study treatment for reasons other than treatment failure and have not withdrawn consent from overall study participation, should continue to be followed for disease response assessments until the time of disease progression/relapse or the initiation of a new treatment regimen. Patients who have stopped FT-2102 treatment for HSCT should continue to be followed until disease progression/ relapse. This information should be documented on the appropriate eCRF page.

6.1.26 Survival Follow-up

After a patient discontinues or completes study treatment, the study site may be requested to contact the patient approximately every 3 months to collect survival status and data pertaining to any other alternative anti-neoplastic therapy. Patients enrolled in the Phase 1 dose-escalation/

dose-expansion stages may have survival follow-up performed for up to 12 months from C1D1 or 28 days after administration of last dose of drug (whichever is longer). Patients enrolled in the Phase 2 cohorts may have survival follow-up for up to 36 months from C1D1 or 28 days after administration of last study drug (whichever is longer).

6.2 Safety

Safety variables to be assessed include: AEs, clinical laboratory tests, vital signs measurements, physical examination findings, and ECG readings (see manual for details of Holter monitoring procedures).

6.2.1 Data Monitoring Committee

Close monitoring of serious safety events as they are reported is conducted by the medical monitor. Serious and non-serious adverse event review is conducted regularly by the medical monitor through monthly listing review. Safety events are also reviewed during regular study conduct meetings between the medical monitor, the clinical team, pharmacovigilance, and the participating investigators.

These study-conduct meetings during the Phase 1 component of this trial include bi-weekly internal review meetings to monitor study progress/safety events and bi-weekly teleconferences with investigators. For the Phase 2 component of the trial monthly meetings with investigators are held.

Periodic safety reviews by Forma's internal DMC, consisting of the clinical study team, pharmacovigilance, and medical monitors not directly involved in the conduct of Study 2102-HEM-101, also occur.

This internal DMC meets at least bi-annually to review safety listings and on an ad hoc basis in response to new safety signals to rapidly assess overall risk to participants. The outcome of these internal DMC meetings, when relevant, is quickly communicated to study investigators so they may share current risk information with their patients and collect updated informed consent forms, if appropriate.

6.3 Bone Marrow Aspirate and/or Biopsy

A bone marrow aspirate for clinical purposes should be obtained from each patient prior to initiating study treatment (baseline) and while on treatment at the time of response assessment (as per Section 4.3).

Bone marrow materials prepared according to the guidelines in the laboratory manual will meet specifications to enable central testing (where indicated) for mutational analysis (including confirmation of presence of IDH1-R132 mutation). Bone marrow biopsy may be used for onstudy disease assessment when bone marrow aspirate is a dry tap.

Refer to the laboratory manual for additional instructions on collecting and processing bone marrow aspirates and biopsies.

6.4 Pharmacokinetics

Note: As of Protocol Version 7/ Amendment 6, PK samples are no longer being collected.

The plasma PK collections will be performed as detailed in Table 4. Blood samples will be collected. The actual time of blood collection must be documented in the respective form, and any deviations outside of the time limits must be commented upon. The scheduled blood sampling times will be used for the PK analysis; however, any deviations outside the limits (real times) are relevant and the data sets will be adjusted for the PK evaluations and the real times will be used.

A laboratory manual will be provided with instructions for collecting and processing of the samples.

Table 4 Pharmacokinetic Sampling Times: FT-2102

Cycle	Day	Sample	Collection Times ^a	Phase 1 Patients	Phase 2 Patients (24 hr Holter Monitoring)	Phase 2 Patients (No 24 hr Holter Monitoring)
	1	1	Predose	X	X	X
		2	30 minutes after dosing (+/- 5 minutes)	X	X	
		3	1 hr after dosing (+/- 5 minutes)	X	X	
		4	2 hr after dosing (+/- 15 minutes)	X	X	
1		5	4 hr after dosing (+/- 15 minutes or 2 hours ^b)	X	X	X
		6	8 hr after dosing (+/- 30 minutes)	X	X	
	2	1	Predose	X	X	
	8, 15, and 22	1	Predose	X		
	1	1	Predose	X	X	X
		2	30 minutes after dosing (+/- 5 minutes)	X	X	
		3	1 hr after dosing (+/- 5 minutes)	X	X	
		4	2 hr after dosing (+/- 15 minutes)	X	X	
2		5	4 hr after dosing (+/- 15 minutes)	X	X	
		6	8 hr after dosing (+/- 30 minutes)	X	X	
	2	1	24 hrs after C2D1 dosing (+/- 2 hrs)	X	X	
	4	1	Predose [72 hrs after C2D1 dosing (+/- 4 hrs)]	X ^c		
	15	1	Predose	X		
3 and 4	1	1	Predose	X	X	X
Random	TBD	1	Collected in the setting of potential treatment-related AE		X	X

^a PK sampling times are specific for FT-2102.

b +/- 15 minutes for Phase 1/ Phase 2 Holter Monitor and +/- 2 hours for Phase 2.

^c Performed in patients participating in the dose-expansion stage only.

Plasma concentration data will be used to determine the following PK parameters:

- AUC Area under the concentration curve
- C_{max} Maximum plasma concentration
- T_{max} Time to maximum plasma concentration
- $t_{1/2}$ Terminal elimination half life
- CL/F Total body clearance
- V_d/F Apparent volume of distribution

6.5 Pharmacodynamics

Note: As of Protocol Version 7/ Amendment 6, PD samples are no longer being collected.

Peripheral blood samples for exploratory PD assessments will be collected at the specified times detailed in Table 5. Blood samples will be collected. The actual time of blood collection must be documented in the respective form and any deviations outside of the time limits must be commented upon.

The scheduled blood sampling times will be used for the PD biomarker analysis; however, any deviations outside the limits (actual times) are relevant and the data sets will be adjusted for the PD evaluations and the actual times will be used.

A laboratory manual will be provided with instructions for collecting and processing of the samples.

Cycle	Days	Sample	Collection Times	Phase 1 Patients	Phase 2 Patients (24 hr Holter Monitoring)	Phase 2 Patients (No 24 hr Holter Monitoring)
Screening	NA	1	Predose	X		
	1	1	Predose	X	X	X
	2	1	Predose	X		
1	8	1	Predose	X		
	15	1	Predose	X		
	22	1	Predose	X		
	1	1	Predose	X	X	X
2	2 ª	1 ^b		X		
2	4ª	1 ^b	Predose	X		
	15	1 ^b	Predose	X		
3 and 4	1	1	Predose	X	X	X

Table 5 Pharmacodynamic Sampling Times: FT-2102 (Single Agent) and FT-2102 plus Azacitidine or Low-Dose Cytarabine (Combination)

